## 3.5 POST-TREATMENT EVALUATIONS

All post-treatment visit(s) may be completed by remote visit with a member of the study team (e.g., if the participant is not able to return to the NIH CC). Remote visits will be conducted in by phone, email or other NIH approved remote platform used in compliance with local policy, including M20-1. Required labs/scans can be obtained by a local provider, with results sent for review and any suggested management by the study team. A participant may be referred to their local provider or asked to come to the NIH CC for an in-person assessment, if clinically indicated, and at the discretion of the investigator; otherwise, physical exams are not required at these time points. In the case of any visits with participants' local providers, records will be obtained for the research records. Remote contact not necessary if participant seen at study site.

### 3.5.1 End of Treatment/Disease Progression Visit

When a participant completes all 6 cycles of treatment or discontinues early, all applicable activities scheduled for the End of Treatment Visit/PD should be performed at the time of discontinuation ([Appendix D](#)).

Some procedures indicated in Study Calendar should be done only in case of PD. This visit should take place as soon as possible after the last administration of study drug (no more than 30 [+/- 7] days). If a new anti-neoplastic therapy is to be initiated, this visit should occur before starting the new therapy. In cases where treatment was on hold, the visit should occur no more than 30 (+/- 7) days after the date participant is taken off treatment, and if needed may coincide with the 30-day safety follow up visit (as needed).

### 3.5.2 30-Day Safety Follow-Up Visit

The safety follow-up visit should occur approximately 30 days after the end of the last cycle; or before the initiation of a new anti-cancer treatment, whichever comes first. Participants with an AE of Grade > 1 will be followed until the resolution of the AE to Grade 0-1 or until the beginning of a new anti-neoplastic therapy, whichever occurs first.

### 3.5.3 Follow-Up Visits – Prior to Disease Progression

Participants who complete trial therapy or discontinue trial treatment for a reason other than disease progression will move into the Follow-Up Phase and should be assessed as below by clinical evaluation and radiologic imaging to monitor status. Every effort should be made to collect information regarding disease status until the start of new anti-neoplastic therapy, disease progression, death, or withdrawal/end of the study.

In follow-up post-treatment prior to disease progression, participants will be seen at the following time points:

- Every 3 months during post treatment year 1 (+/- 14 days)
- Every 4 months during post treatment year 2 (+/- 14 days)
- Every 6 months during post treatment year 3 (+/- 21 days)
- Every 1 year during post treatment years 4-10 (+/- 28 days)

All required testing is as noted in the Study Calendar ([Appendix D](#)).

**NOTE:** Restaging scans should only be performed based on involved sites of disease at baseline (e.g., patients with CNS disease only should undergo restaging MRI brain while those with systemic disease should also undergo CT C/A/P. Patients who achieve CR by post-treatment PET only need repeat PET imaging as clinically indicated).

### 3.5.4 Follow-Up Visits – Survival/Post-Disease Progression

Once participants progress or start use of alternative antineoplastic therapy, they will be contacted, approximately every 3 months (+/- 14 days), for a maximum of 10 years to assess survival and the use of alternative antineoplastic therapy and stem cell transplant until withdrawal/end of the study (Section [3.8.2](#)).

## 3.6 STUDY CALENDAR

See [Appendix D](#). Appendix D: Study Calendar

### **3.7 COST AND COMPENSATION**

#### **3.7.1 Cost**

NIH does not bill health insurance companies or participants for any research or related clinical care that participants receive at the NIH Clinical Center. If some tests and procedures performed outside the NIH Clinical Center, participants may have to pay for these costs.

#### **3.7.2 Compensation**

Participants will not be compensated on this study.

#### **3.7.3 Reimbursement**

The NCI will cover the costs of some expenses associated with protocol participation. Some of these costs may be paid directly by the NIH and some may be reimbursed to the participant/guardian as appropriate. The amount and form of these payments are determined by the NCI Travel and Lodging Reimbursement Policy.

### **3.8 CRITERIA FOR REMOVAL FROM PROTOCOL THERAPY AND OFF-STUDY CRITERIA**

Prior to removal from study, every effort must be made to have all participants complete a safety visit approximately 30 (+7) days following the last dose of study therapy. Additional safety visits and follow-up will continue as per Section [3.5](#).

#### **3.8.1 Criteria for removal from protocol therapy**

- Disease progression
- Unacceptable adverse event(s) as explained in Section [3.3](#)
- Delay of treatment for more than 6 weeks, unless it is felt by the Principal Investigator to be in the participant's best interests to remain on study in exceptional circumstances.
- Participant requests to be withdrawn from the treatment
- Participant requires a prohibited concomitant medication as explained in Section [4.3](#)
- Participant HBV DNA level exceeds 100 IU/mL while on antiviral medication as explained in Section [4.1.2](#)
- Pregnancy
- Investigator's discretion
- Study is cancelled for any reason

#### **3.8.2 Off-Study Criteria**

- Screen failure and/or failure to maintain eligibility (i.e., between enrollment and day 1 of study treatment)
- Completion of 10 years follow-up period
- Participant requests to be withdrawn from the study
- Lost to follow-up
- Death
- Study is cancelled for any reason

### 3.8.3 Lost to Follow-up

A participant will be considered lost to follow-up if he or she fails to report for two (2) scheduled visits and is unable to be contacted by the study site staff.

The following actions must be taken if a participant fails to return to the clinic for a required study visit:

- The team will attempt to contact the participant and reschedule the missed visit within 5 business days and counsel the participant on the importance of maintaining the assigned visit schedule and ascertain if the participant wishes to and/or should continue in the study.
- Before a participant is deemed lost to follow-up, the investigator or designee will make every effort to regain contact with the participant (where possible, 3 telephone calls and, if necessary, an IRB-approved certified letter to the participant's last known mailing address or local equivalent methods). These contact attempts should be documented in the participant's medical record or study file.
- Should the participant continue to be unreachable, he or she will be considered to have withdrawn from the study with a primary reason of lost to follow-up.

## 4 CONCOMITANT MEDICATIONS/MEASURES

### 4.1 PERMITTED CONCOMITANT MEDICATIONS

Supportive medications in accordance with standard practice (such as for emesis, diarrhea, etc.) are permitted. Use of neutrophil growth factors (filgrastim and pegfilgrastim) is permitted per institutional policy and in accordance with the ASCO guidelines. Transfusions may be given in accordance with institutional policy.

#### 4.1.1 For Participants on pre-treatment corticosteroids

Pretreatment dexamethasone (or other corticosteroid) is part of the standard treatment for participants with CNS mass lesions. Dexamethasone or other steroid doses will be reduced and/or terminated as early as possible according to safe medical practice.

#### 4.1.2 Prophylaxis of Hepatitis B reactivation

Participants who are positive for either Hepatitis B core antibody (HBcAb) or Hepatitis B surface antigen (HBsAg) and not acutely infected are at varying risk for reactivation of Hepatitis B especially when combined with novel agents like ibrutinib and rituximab. Participants may be included in the study provided that they have HBV DNA levels below the World Health Organization's cutoff of 100 IU/mL prior to starting therapy. These participants will be treated with entecavir (or equivalent) to prevent hepatitis B reactivation and should have HBV DNA levels obtained monthly during treatment, and at: End of Treatment, 30 Day Post-Treatment Safety Visit; and every 3 months for 12 months after the last cycle of therapy by means of real-time PCR with the use of an assay that has a sensitivity of at least 10 IU/mL.

If the HBV DNA assay becomes positive during combination therapy, study treatment should be held, and the participant should be immediately referred to a gastroenterologist or hepatologist for management recommendations.

If a participant's HBV DNA level exceeds 100 IU/mL while the participant is receiving antiviral medication, study treatment must be permanently discontinued

#### 4.1.3 Prophylaxis of *Pneumocystis jiroveci* (previously *Pneumocystis carinii*)

All participants will receive prophylaxis for *Pneumocystis Jiroveci* during VIPOR therapy. Trimethoprim/sulfamethoxazole 1 double strength (DS) tablet by mouth for three days each week. Monday, Wednesday, Friday is the preferred schedule. Participants allergic to either component may receive inhaled pentamidine 300 mg once a month or other standard treatments.

#### 4.1.4 Nausea

Medications to prevent nausea and vomiting are permitted as clinically indicated.

#### 4.1.5 Febrile Neutropenia

This is a life-threatening complication requiring urgent broad-spectrum antibiotics. Management may be as an inpatient or outpatient depending on the clinical situation.

#### 4.1.6 Symptomatic anemia

This should be treated with appropriate red blood cell support. Only irradiated leukodepleted blood products should be used.

#### 4.1.7 Thrombocytopenia

In the absence of bleeding or planned invasive procedures, platelet transfusions should be given for platelets  $< 10,000/\text{mm}^3$ . If invasive procedures are planned or the participant develops bleeding, platelet transfusions should be administered in accordance with standard of practice, usually maintaining a platelet count  $> 50,000/\text{mm}^3$ .

#### 4.1.8 Central Venous Access

Central Venous Access may be used for administration of intravenous medications and for drawing blood samples. Possible lines include:

- Temporary internal jugular line;
- PICC lines via the brachial vein;
- semi-permanent HICKMAN,
- GROSHONG catheters; or
- medi-port implanted devices.

All devices will have nursing supervision to include participant self-care and cleaning/flushing of the devices.

#### 4.1.9 Venous Thromboembolism Prophylaxis

The use of lenalidomide has been associated with the development of venous thromboembolism, including deep venous thrombosis and pulmonary embolism. Ibrutinib has been associated with increased risk of bleeding, including serious intracranial hemorrhage. VTE risk assessment will be performed in all participants at baseline and the risks and benefits of anticoagulation with aspirin or low molecular weight heparin will be assessed by the investigators and discussed with the participant. General risk factors for participants with cancer include, but are not limited to underlying disease, family history, age, obesity, immobilization, hormonal therapy, central venous

catheter, recent DVT, sex, renal dysfunction, and certain chemotherapy-based regimens. It is not known whether prophylactic anticoagulation or anti-platelet therapy prescribed in conjunction with Revlimid® may lessen the potential for venous thromboembolism. It is up to the discretion of the Investigator after consideration of the participant's individual risk/benefit profile whether to institute VTE prophylaxis.

#### **4.2 MEDICATIONS TO BE USED WITH CAUTION**

Concomitant medications that fall into the categories below could potentially lead to adverse reactions and should be considered cautionary (except where noted). If a potential study participant is taking any of the medications in the categories described below, the investigator must assess and document the use of medications known or suspected to fall in the following medication categories:

- Moderate/weak CYP3A inducers such as efavirenz and oxcarbazepine
- CYP2C8 substrates such as thiazolidinediones (glitazones) and select statins (because of expected inhibition of the metabolism of CYP2C8 substrates by venetoclax)
- CYP2C9 substrates such as tolbutamide (because of expected inhibition of the metabolism of CYP2C9 substrates by venetoclax). It is recommended to exclude CYP2C9 substrates with a narrow therapeutic index such as phenytoin.

For participants taking digoxin, periodic monitoring of digoxin plasma levels is recommended due to increased Cmax and AUC with concomitant lenalidomide therapy (please see lenalidomide product insert).

Participants taking concomitant therapies such as erythropoietin stimulating agents or estrogen containing therapies, may have an increased risk of venous thromboembolism with lenalidomide (please see lenalidomide product insert).

##### **4.2.1 CYP3A Inhibitors/Inducers**

Venetoclax and ibrutinib are metabolized primarily by CYP3A4. Avoid co-administration with strong CYP3A4 inhibitors or moderate CYP3A inhibitors and consider alternative agents with less CYP3A inhibition. If a strong CYP3A inhibitor must be used, reduce ibrutinib dose to 280 mg or withhold treatment temporarily. Participants should be monitored for signs of ibrutinib toxicity. No dose adjustment is required in combination with mild or moderate inhibitors. Avoid grapefruit and Seville oranges during ibrutinib treatment, as these contain moderate inhibitors of CYP3A.

Avoid concomitant use of strong CYP3A inducers (e.g., carbamazepine, rifampin, phenytoin, and St. John's Wort). Consider alternative agents with less CYP3A induction.

A list of inhibitors, inducers, and substrates may be found at: <https://drug-interactions.medicine.iu.edu/MainTable.aspx>

Although the ibrutinib Package Insert (dated May 2022) indicates to dose reduce ibrutinib to 280 mg daily in participants with B-Cell malignancies if it is co-administered with a moderate CYP3A inhibitor and results in toxicity, in this protocol dose modifications are different because ibrutinib is being used indefinitely where dose interruptions are more clinically feasible. In our study of combination therapy, we use time-limited therapy and holding doses even for just a few days can have a detrimental effect on efficacy. Furthermore, this study is testing the agent in patients where lymphoma is involving the central nervous system (CNS). Our data with ibrutinib

suggests that higher doses to achieve CNS penetration are critical to efficacy. In other scenarios (such as CLL and MCL), one gets full BTK occupancy at lower doses, so it is less of an issue. We do not think that we should make any changes to our dose modification tables for these scientific reasons and do not anticipate additional toxicity based on this decision.

#### 4.2.2 QT Prolonging Agents

Any medications known to cause QT prolongation should be used with caution; periodic monitoring with electrocardiograms and electrolytes should be considered.

#### 4.2.3 Drugs That May Have Their Plasma Concentrations Altered by Ibrutinib

*In vitro* studies indicated that ibrutinib is not a substrate of P-glycoprotein (P-gp) or other transporters, except OCT2. Ibrutinib is a mild inhibitor of P-gp and breast cancer resistance protein (BCRP). Ibrutinib is not expected to have systemic drug-drug interactions with P-gp substrates. However, it cannot be excluded that ibrutinib could inhibit intestinal P-gp and BCRP after a therapeutic dose. There is no clinical data available; therefore, to avoid a potential interaction in the GI tract, narrow therapeutic range P-gp or BCRP substrates such as digoxin or methotrexate should be taken at least 6 hours before or after ibrutinib. Inhibition of the BCRP pathway may increase exposure to drugs that undergo BCRP mediated hepatic efflux, such as rosuvastatin.

#### 4.2.4 Antifungal Agents

Given the overlapping toxicity of these targeted agents as well as other immunosuppressive therapies, such as steroids, there is an increased risk of infectious complications, including potential invasive fungal infections. Participants on this study will be undergoing frequent imaging for response evaluation and the investigators will also evaluate these imaging studies for potential infectious complications, including possible invasive fungal infection. Further clinical work-up may include, but is not limited to, peripheral blood analysis for fungal blood markers and/or bronchoscopy with bronchoalveolar lavage (BAL) testing for fungal markers/cultures and other infectious pathogens.

Antifungal therapy with echinocandins, such as micafungin or caspofungin, as well as treatment with ambisome are permitted on study if deemed clinically appropriate. Due to the strong inhibition of CYP3A with certain azoles (e.g., voriconazole, posaconazole, itraconazole or ketoconazole), treatment with any of these agents will require dose reduction of ibrutinib as per Section 4.2.1. Prophylactic antifungals will not be routinely used given the low estimated risk of fungal infections with cyclic, non-continuous dosing of targeted agents

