### 4.3 PROHIBITED CONCOMITANT MEDICATIONS

#### 4.3.1 Prohibited Therapy

Participants who require the use of any of the excluded therapies listed below will be discontinued from study treatment.

Use of the following therapies is prohibited during the study:

- Immunotherapy
- Hormone therapy (other than contraceptives, hormone replacement therapy, or megestrol acetate)
- Any therapies intended for the treatment of lymphoma whether FDA approved or experimental (outside of this study)
- Warfarin or warfarin derivatives

The following concomitant medications are not allowed from 7 days prior to the first dose of study drugs and during study drug administration:

- Strong CYP3A4 inhibitors such as voriconazole, ketoconazole, and clarithromycin
- Strong CYP3A4 inducers such as rifampin and carbamazepine

A comprehensive list of inhibitors, inducers, and substrates may be found at: <https://drug-interactions.medicine.iu.edu/MainTable.aspx>. Pretreatment corticosteroids for CNS disease is permitted before entering this study as explained in Section [2.1.2.4](#).

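### Sections 4.2.1 and 4.2.4 let ibrutinib continue at 280 mg beside a strong CYP3A inhibitor that Section 4.3.1 does not allow, and this route gives no action for venetoclax

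*Combined protocol and SAP*

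**What the plan says.** All references are to the combined protocol and SAP.

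**Text that lets treatment continue.** Section 4.2.4 covers antifungal treatment on study. For the strong-inhibitor azoles it says: "voriconazole, posaconazole, itraconazole or ketoconazole), treatment with any of these agents will require dose reduction of ibrutinib as per Section 4.2.1". Section 4.2.1 supplies the rule: "If a strong CYP3A inhibitor must be used, reduce ibrutinib dose to 280 mg or withhold treatment temporarily". The next sentence is "Participants should be monitored for signs of ibrutinib toxicity". The note under Table 4 in Section 3.3.3 also sends the reader to 4.2.1 for managing ibrutinib in this situation.

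**Text that bars the combination.** Section 4.3.1 says "The following concomitant medications are not allowed from 7 days prior to the first dose of study drugs and during study drug administration", and its list includes "Strong CYP3A4 inhibitors such as voriconazole, ketoconazole, and clarithromycin". Sections 14.1.4 (venetoclax) and 14.2.4 (ibrutinib) each describe use with strong CYP3A inhibitors as contraindicated, then point to Sections 4.2 and 4.3. Section 4.2.1, after stating that both drugs are metabolized mainly by CYP3A4, opens with general advice: "Avoid co-administration with strong CYP3A4 inhibitors or moderate CYP3A inhibitors and consider alternative agents with less CYP3A inhibition".

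**Removal.** Section 4.3.1 begins with "Participants who require the use of any of the excluded therapies listed below will be discontinued from study treatment", followed by a list of prohibited therapies and then the separate list of concomitant medications that contains the strong inhibitors. Section 3.8.1 removes a participant who needs a concomitant medication prohibited under 4.3.

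**Venetoclax.** The planned dose is 800 mg on days 1-14 (Section 3.2). Section 3.3.2 and Tables 1 and 2 provide holds and reductions to 600 mg and 400 mg, driven by examination findings, toxicities and laboratory results.

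**The concern.** An investigator who needs voriconazole for a fungal infection finds two incompatible instructions. Section 4.2.4 requires a lower ibrutinib dose, which presumes that treatment goes on. Section 4.3.1 says the azole may not be given while study drug is being taken. No precedence between them is stated.

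The second problem is venetoclax. Section 4.2.1 recognises it as a CYP3A4 substrate, but the only dose given and the only toxicity named for monitoring are for ibrutinib. Section 4.2.4 does not mention venetoclax in this context. Someone who follows 4.2.4 as written could halve ibrutinib and leave venetoclax at full dose, in a combination that 14.1.4 calls contraindicated.

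Safety and tolerability are the primary objective, and the participants concerned would already be infected and immunosuppressed. A dosing rule that can lead to a combination barred elsewhere in the same protocol should not stay in force.

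**Working it through.** This is a comparison of instructions. The only arithmetic is dose fractions and a check that the design figures are unaffected.

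**1. Instructions side by side, for a participant who needs a strong CYP3A inhibitor**

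| Section | Ibrutinib | Venetoclax |
|---|---|---|
| 3.3.3, note under Table 4 | refers to 4.2.1 | silent |
| 4.2.1, general advice | avoid | avoid |
| 4.2.1, branch (a) | reduce to 280 mg | silent |
| 4.2.1, branch (b) | withhold temporarily | not named; can be read as included |
| 4.2.4 | reduce as in 4.2.1 | silent |
| 3.3.2, Tables 1-2 | not applicable | toxicity-driven only |
| 4.3.1 | not allowed | not allowed |
| 14.1.4 / 14.2.4 | contraindicated, see 4.2 and 4.3 | contraindicated, see 4.2 and 4.3 |

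Branch (b) is compatible with 4.3.1, because no study drug is given while the inhibitor is. Branch (a) and the azole sentence in 4.2.4 are not compatible with it.

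**2. Overlap of named drugs.** Section 4.2.4 names voriconazole, posaconazole, itraconazole and ketoconazole. Section 4.3.1 names voriconazole, ketoconazole and clarithromycin as examples. Two of the four azoles in 4.2.4 are therefore named as not allowed. The other two fall under the same class, since 4.2.4 itself describes all four as strong inhibitors.

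**3. Doses under a literal reading of 4.2.4**

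- Ibrutinib: 280/560 = 50% of plan.
- Venetoclax, no change stated: 800/800 = 100% of plan.
- Table 2 levels for comparison: 600/800 = 75% and 400/800 = 50%, both reached through toxicity only.

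These are nominal doses. The documents do not say how much a strong inhibitor raises exposure to either drug.

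**4. Design figures (Section 10.2).** With n = 10 and success declared at 7 or more:

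- p = 0.5: (120 + 45 + 10 + 1)/1024 = 176/1024 = 0.1719, matching 17.2%.
- p = 0.8: 0.2013 + 0.3020 + 0.2684 + 0.1074 = 0.8791, matching 87.9%.

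Neither depends on the CYP3A rule.

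**The case against.** The best defence is that 4.2.1 has a familiar structure: a general instruction to avoid, then a narrow exception when a strong inhibitor cannot be avoided. On that view 4.3.1 merely lacks a cross-reference, and 14.1.4 and 14.2.4 point to 4.2 and so admit the exception. Part of this stands. The two Section 14 statements are not independent bars, and the core conflict is 4.2 against 4.3.1. But 4.3.1 contains no carve-out, and even if the exception is accepted for ibrutinib it supplies nothing for venetoclax.

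A reader might infer that the plan provides no venetoclax hold at all. The documents do not support that. The withhold option in 4.2.1 is not limited to ibrutinib, and the paragraph opens with both drugs. The gap is confined to the reduce branch.

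A reader might also infer that removal from treatment is the only permitted outcome. Section 3.8.1 leans that way, but the removal sentence in 4.3.1 can be read as covering only its first list, so the text does not settle it.

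Existing safeguards also count: continuous strong-inhibitor need is excluded at entry (2.1.2.4), echinocandins and ambisome are permitted, azole prophylaxis is not routine (4.2.4), blood counts and chemistry are weekly, and toxicity triggers venetoclax holds (Table 1). They make the event rare and limit its consequences. They act after exposure, however, and do not resolve the contradiction.

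**Conclusion.** The point holds as a conflict between dosing instructions with a safety consequence. Reduce-and-continue in 4.2.1 and 4.2.4 cannot be reconciled with 4.3.1 as worded, and on that route venetoclax has no stated action. Its size is limited to what the documents show: ibrutinib at 50% of plan, venetoclax possibly at 100%, in a situation that should be rare. No rate of strong-inhibitor use and no exposure increase can be derived, so a reader who infers a quantified overdose or a known toxicity rate goes further than the text allows.

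The hold option is already in the protocol. It may be passed over, because 4.2.1, when explaining its approach to moderate inhibitors, remarks that "holding doses even for just a few days can have a detrimental effect on efficacy". That remark was not written about strong inhibitors, so this is a plausible effect and not a demonstrated one.

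The conclusion assumes that 4.3.1 means what it says during study drug administration, and that an investigator may act on 4.2.4 without consulting 4.3.1 or Section 14. The decision rule and its operating characteristics are unaffected.

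**What to change.** Amend the wording as follows.

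- **4.2.1 and 4.2.4:** replace reduce-and-continue with the existing withhold option, stated explicitly for both venetoclax and ibrutinib for as long as a strong CYP3A inhibitor is required. State when dosing may resume after the inhibitor stops; the sponsor should set the interval.
- **3.3.2 and 3.3.3:** cross-refer to this rule.
- **4.3.1 and 3.8.1:** align them so that a temporary need leads to a hold. Removal should follow only under the existing 6-week rule, including the principal investigator's exception in 3.8.1.
- **3.3.1:** say that the 6-week allowance, now tied to recovery from toxicity, also covers this hold, and that holding both drugs does not count as discontinuing two drugs.

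The amendment adds no procedures. Its clinical cost is a possible short interruption of therapy, which 4.2.1 suggests may reduce efficacy; the antifungals already permitted in 4.2.4 can avoid some holds. There is also a small statistical cost. Success in Section 10.4.2 requires completing at least 2 cycles without discontinuing for toxicity. Rarely, a participant held or removed early could fail to complete 2 cycles for another reason, and with 10 evaluable participants one such case moves the observed fraction by 1/10. The 7-of-10 threshold, the 17.2% and the 87.9% stay as they are.
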